EFFECT OF HYPERBARIC OXYGEN THERAPY ON THE DEVELOPMENT OF AIRWAY STENOSIS IN PATIENTS WITH SEVERE AIRWAY EXUDATIVE PLAQUES EARLY AFTER LUNG TRANSPLANTATION

[name], [name], [name]

NCT02363959

BACKGROUND:

Central airway stenosis (CAS) is seen in 8-15% patients after lung transplantation.^{1,2} Development of airway stenosis can cause decline in pulmonary function, increased respiratory symptoms, increased infections, and occasionally death³. The lungs are unique in containing dual circulatory supply from the pulmonary circulation which is reanastomosed during lung transplantation, and the bronchial circulation which is not. Perfusion of the large airways is thought to occur via retrograde flow from vascular plexus' between the bronchial and pulmonary arterial circulation until new collateral circulation to the bronchial arterial system can develop in the weeks following transplantation³. Assessment of large airways perfusion has been surprisingly poorly studied, but development of airways ischemia post-transplantation is thought to be involved with development of CAS and other airway complications, opportunistic infections, particularly fungal infections, and possibly with chronic allograft rejection.^{1,4}

CAS is managed with balloon dilation followed by airway stent placement for recurrent stenosis.⁴⁻⁷ A limited number of retrospective studies have shown that the treated airway complications do not affect survival.^{1,8} However, these airway complications prolong mechanical ventilation, hospital and ICU length of stay, increase cost, and adversely affect quality of life³.

Patients undergo frequent bronchoscopy in the weeks and months following lung transplantation. Many, if not most patients develop some element of necrotic desquamation of the epithelium locally referred to as “exudative plaques” or “pseudomembranes” in the large central airways two to four weeks after lung transplantation. There is a spectrum of involvement, but prior work would suggest that up to 50% of patients who develop the most severe manifestations of these plaques go on to develop some form of large airway complication, most commonly CAS⁹. Our local experience supports this observation. There is no established intervention available for these patients, however, because airway ischemia is thought to play an important role in this process, our group has treated a small group of patients with hyperbaric oxygen therapy (HBOT) with anecdotal improvement in the appearance of the airways as well as a perceived reduction in frequency and severity of anticipated airway complications in some patients.

HBOT is defined as compression of the body with at least 1.4 atmospheres absolute pressure (ATA) of pure oxygen. It is believed to decrease inflammation, control infection, enhance perfusion and promote wound healing.¹⁰ It is used for treatment of chronic refractory wounds, including diabetic, small arterial and radiation-related wounds, as an adjunct to surgical reconstruction wounds, flaps or grafts, and chronic osteomyelitis.¹¹⁻¹³ It has been shown to improve wound healing and decrease the need for limb amputations in diabetic patients. HBOT is not necessary or recommended for normal or uncompromised grafts or flaps, but where the graft or flap is compromised by hypoxia, ischemia or congestion, HBO₂ has been shown to be extremely useful in graft salvage (14). Our preliminary experience with HBOT in lung transplant patients with severe pseudomembranes has been encouraging. We perceive that use of this technique has hastened resolution of the pseudomembranes, improved infectious complications and decreased the incidence of CAS. Based on this preliminary experience we feel systematic examination of this approach is warranted.

OBJECTIVES:

The objective of this study is to evaluate the effect of HBOT on subsequent airway complications in lung transplant recipients with evidence of ischemic changes in the large airway epithelium. Study subjects with extensive desquamation (exudative plaques) of the large airway epithelium in the early post-transplant period will be randomized to HBOT or usual care and followed clinically for 12 months following randomization. We hypothesize that HBOT will decrease the number of airway complications in the treated subjects.

SUBJECT ENROLLMENT

Standard post-lung transplantation care includes a bronchoscopy with transbronchial lung biopsy at 1 month after surgery. We believe that it is in this early period, when the neovascularization of the large airways is thought to occur, that subjects are most likely to benefit from HBOT. Patients who are noted to have extensive exudative plaques (grade 3 or 4) at their 1 month bronchoscopy will be referred for a standard follow-up bronchoscopy 2 to 3 weeks later. Should the patient show no sign of improvement in their airways, or worsening of the plaques they will be considered eligible for enrollment in the study.

Exclusion Criteria

Exclusion criteria include: use of mechanical ventilation with FiO₂ greater than 40%, use of extracorporeal membrane oxygenation, use of inhaled nitric oxide, presence of pneumothorax, pregnancy, or inability to provide informed consent. In addition, subjects who are deemed to be

too clinically unstable to be transported safely to the hyperbaric facility by their treating physicians will be excluded from enrollment.

Randomization

Once subjects are deemed eligible for enrollment, they will be questioned as to their interest in participating in the study by the treating physician. Those interested will be approached by the study coordinator for informed consent. Once informed consent is obtained, subjects will be randomized to usual care or HBOT by selection of a pre-prepared envelope containing the randomization assignment. We will target a total enrollment of 40 subjects with 1:1 enrollment to either HBOT or usual care.

Subject Compensation

Subjects will not be compensated for participation in the study. However, they will not be charged for hyperbaric treatment or the research biopsies. The airway and rejection surveillance bronchoscopies are part of current standard care in the Duke lung transplant program and are continued accordingly in the study. All participants will be recruited at DUHS.

STUDY PROCEDURES

Hyperbaric Therapy

The HBOT will be performed with the standard HBOT protocol used at Duke for the treatment of compromised grafts and flaps. This is 2 hours of breathing >99% medical grade oxygen inside an air-pressurized chamber at 2 ATA once a day for 20 sessions. These sessions will be scheduled 3-5 times per week, depending on the availability of the patient and the hyperbaric medicine physician. The HBOT procedure used for this study will be identical to that used for clinical practice in the Duke University Health System Center for Hyperbaric Medicine and Environmental Physiology, including the oxygen that is used in the chamber. Patients will receive treatment through the regular clinical hyperbaric service. These are routine, not special, treatment sessions and they will receive them alongside other Duke University Medical Center patients being treated for other reasons. The medical grade oxygen used is a part of the Duke University Health System Center for Hyperbaric Medicine and Environmental Physiology hyperbaric chamber system.

The patients sign the standard Duke informed consent for the administration of HBOT inside the chamber. The primary risks, which each occur in less than 10% of patients, are middle ear barotrauma from the changes in barometric pressure (resolves in a few days) and temporary near-sightedness that may occur after 20 to 30 sessions, and resolves in 2-3 months, but which can rarely leave some persistent myopia that requires a change in eyeglass prescription. The other

risks are very rare (<1%) and include oxygen-induced convulsions, and pneumothorax, and there is a very remote chance of mechanical or electrical failure in the chamber resulting in a fire.

Airway Surveillance

While the patients randomized to receive usual care will not undergo HBOT, both study groups will receive standard serial bronchoscopies for airway clearance and for the collection of bronchoalveolar lavage fluid for culture data, due to the high rate of infection in lung transplant patients. All subjects will undergo the standard surveillance bronchoscopies every 3 to 4 weeks (x3) for clearance of the exudate from the airway, as well as monitoring progression of the airway abnormalities. Additional bronchoscopies will be performed as clinically indicated. Following the completion of the airway surveillance, subjects will revert to the standard rejection surveillance schedule of bronchoscopy every 3 months for the first year post-transplant.

At each surveillance bronchoscopy, subjects will have the standard bronchoalveolar lavage performed for detection of infectious agents. Due to the high evidence of airway infections in patients with severe exudative plaques, a lavage is performed during each bronchoscopy as a part of standard practice to collect microbiologic data. As participants in this study, an, endobronchial biopsy of the airway epithelium will be performed at the main carina to collect a sample of recipient epithelium as well as at the first subcarina for each donor lung. Three samples will be collected from each of the biopsy sites. These samples are small (1 to 2 mm) and are thought to have a minimal clinical risk of minor bleeding associated with the procedure. Biopsy will add roughly 3 minutes total to each procedure. These samples will be used for mRNA extraction to detect expression of genes associated with response to tissue hypoxia.

Measurements and Data Collection

Primary outcomes: Need for airway stent placement and rate of acute rejection in the 12 months of observation as determined by transbronchial lung biopsy.

Secondary outcomes: Include development of airway stenosis, need for balloon bronchoplasty, development of clinically significant pulmonary infection as defined by initiation of antimicrobials to treat the suspected organism, development of airway dehiscence following enrollment in the study, development of bronchiolitis obliterans syndrome, and bronchial epithelial gene expression.

Additional clinical data to be collected will include spirometric data, frequency of hospitalization, hospital days, ICU days, mechanical ventilation days, need for tracheostomy, and survival.

TREATMENT ARM CROSSOVER

Should patients enrolled in the usual care arm develop airway complications such as airway stenosis, dehiscence, or airway malacia, or if the patient fails to improve their exudative plaque score over the period of observation, they may be offered hyperbaric therapy with continued collection of clinical data. Subjects will be eligible for crossover therapy between 8 and 12 weeks after the initial study bronchoscopy.

There are two criteria for a patient to qualify for HBOT crossover treatment. The first criterion is the development of an airway complication, most likely airway stenosis requiring intervention. This is clinically defined by our group as an airway that is no longer traversable with a therapeutic (6.4mm OD) bronchoscope. Other complications are airway dehiscence or malacia (excessive loss of structural integrity). The second criterion is failure of the airway exudate to improve in score severity during the 8 week observation period. This is measured using the scoring system outlined in Table 1.

RISK/BENEFIT ASSESSMENT

It is currently unknown if treatment of patients with severe exudative plaques in the early post-lung transplant period with HBOT will prevent development of large airway complications. Our limited anecdotal experience suggests it may improve outcomes. The risks of the procedure are small and detailed above. The potential benefits are significant since airway stenosis can lead to worse allograft function, increased infections, and occasionally death. Subjects randomized to usual care will be at usual risk of airway complications. Given the clinical equipoise regarding HBOT treatment in lung transplant, we feel this is an ethical treatment decision for this patient population.

COST TO THE SUBJECT

There will be no additional costs to the subject over usual care. The hyperbaric treatment will be provided at no charge to the subjects.

DATA ANALYSIS AND STATISTICAL CONSIDERATIONS

Data analysis will be performed by the primary investigators. Categorical data will be analyzed using Fisher's exact test given the small sample size, while continuous data will be assessed for statistical significance with Student's t-test. Our prior work with airway stenosis in lung transplant recipients documented a 15% rate of stenosis in all transplant patients. Our clinical experience suggests a rate 2 to 4-fold higher in patients with severe ischemic desquamation of

the large airways. Experience with HBOT in this population is limited, but rates of significant airway stenosis may be as low as 10% after therapy. Sample size calculations using a 60% stenosis rate in the usual care group, a 10% stenosis rate in the HBOT group with a p-value of 0.05 suggest that a sample of 14 subjects/group will have an 80% power to detect statistical significance. We will target a total of 40 subjects to allow for subject withdrawal and loss due to the development of critical illness in this tenuous population. Intention to treat analysis will be used for all patients based on initial randomization, with subgroup analysis for the crossover patients for airway stent placement. All biologic samples will be collected by week 6, prior to any patient crossover events.

DATA and SAFETY MONITORING

Data will be stored on a secured Access database located on the PIN station “U” drive in an secured folder. All subject entries will be de-identified using a study assigned identification number. The key to the study identifiers will be kept in a locked file cabinet in the study coordinators office. Database use will be limited to the primary investigators, co-investigators, and the study coordinator.

Primary risks are related to bronchoscopy with minimal risk of bleeding related to the endobronchial lung biopsy, and some discomfort from the bronchoscopy itself which is part of usual post-transplant care. Additional risks of hyperbaric treatment are detailed above and very rare. Any adverse events that occur during the study will be immediately reported to the IRB.

Table 1. Pseudomembrane Scoring System

Stage	Definition
Stage 0	No exudate
Stage 1	Limited to anastomosis
Stage 2	Anastomosis to upper lobe orifice, including medial bronchus intermedius
Stage 3	Involvement of the lower lobe orifice
Stage 4	Covers all visible airways

REFERENCES:

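### Plaque stage (3 or 4) is assessed before randomisation and plausibly affects outcome, but neither the allocation nor the Fisher comparison uses it; the cost is conditional and modest, and the fix is cheap

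*Combined protocol and SAP*

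**What the plan says.** Under Subject Enrollment, candidates are "Patients who are noted to have extensive exudative plaques (grade 3 or 4) at their 1 month bronchoscopy". They have a second bronchoscopy 2 to 3 weeks later, and the entry rule then reads "Should the patient show no sign of improvement in their airways, or worsening of the plaques they will be considered eligible". Table 1 defines Stage 3 as "Involvement of the lower lobe orifice" and Stage 4 as "Covers all visible airways". I take the grade in the entry rule to be the Table 1 stage.

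On allocation, the Randomization paragraph says "subjects will be randomized to usual care or HBOT by selection of a pre-prepared envelope containing the randomization assignment", and "We will target a total enrollment of 40 subjects with 1:1 enrollment to either HBOT or usual care". It names no stratification factor or blocking.

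The Data Analysis section assigns Fisher's exact test to categorical data and Student's t-test to continuous data. The only subgroup it names is the crossover patients. Baseline stage does not appear.

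Two statements bear on prognosis. The Background says "There is a spectrum of involvement, but prior work would suggest that up to 50% of patients who develop the most severe manifestations" go on to a large airway complication. The Data Analysis section starts from a 15% stenosis rate in all transplant patients and adds: "Our clinical experience suggests a rate 2 to 4-fold higher in patients with severe ischemic desquamation of" the large airways.

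**The concern.** The trial rests on the idea that worse plaques mean more airway complications, and Table 1 is its only severity scale. Failure to improve on that scale is also one of the two crossover criteria. A score that governs entry and crossover is a natural candidate to balance between arms, and it is available before the envelope is opened.

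With about 20 patients per arm, chance can place clearly more Stage 4 patients in one arm. If Stage 4 carries more risk, part of any difference in stents or stenosis would then reflect stage, and the plan has no prespecified comparison that separates the two. Small differences count at this size: 10/20 v 3/20 gives a two-sided Fisher p of 0.041, and 9/20 v 3/20 gives 0.082.

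**Working it through.** **Inputs from the protocol.** 40 patients at 1:1, so 20 per arm; stenosis 60% under usual care and 10% under HBOT; alpha 0.05 (two-sided assumed); 80% power with 14 per group; Fisher's exact test.

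**Inputs assumed.** The share of Stage 4 among entrants (20% to 50%) and the risk gap between Stages 4 and 3 (10, 20 or 30 points). The documents give neither.

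**1. The plan's own figure.** Pooled normal formula, mean rate 0.35:

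n = [1.960 × √(2 × 0.35 × 0.65) + 0.842 × √(0.24 + 0.09)]² / 0.50² = (1.322 + 0.483)² / 0.25 ≈ 13.04, rounded up to 14.

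This matches the stated 14 per group. With 20 per arm, the standard error of the risk difference is √(0.24/20 + 0.09/20) = 0.128, about 13 points, against a planned difference of 50.

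**2. How often stage is unbalanced.** With K Stage 4 patients among 40, the number X in one arm of 20 is hypergeometric (40, K, 20). The arms differ by |2X − K|.

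| Stage 4 among 40 | Differ by 4 or more | Differ by 6 or more |
|---|---|---|
| 8 (20%) | 23.5% | 4.4% |
| 12 (30%) | 30.1% | 8.2% |
| 16 (40%) | 33.3% | 10.5% |
| 20 (50%) | 34.3% | 11.3% |

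Both directions are counted; half of each figure favours HBOT.

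**3. Size of the shift with no HBOT effect.** Shift = (difference in Stage 4 count / 20) × stage gap.

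| Difference | Gap 30 | Gap 20 | Gap 10 |
|---|---|---|---|
| 4 (0.20) | 6 points | 4 points | 2 points |
| 6 (0.30) | 9 points | 6 points | 3 points |

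At a 50:50 mix, the mean absolute shift is 3.7 points at the 30-point gap and 2.5 at the 20-point gap.

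**4. Size of the shift under the planned effect.** Step 3 needs the same gap in both arms. With a 10% HBOT rate and a 50:50 mix, the widest possible HBOT-arm gap is 20 points (0% and 20%). A 12 v 8 split moves each arm's Stage 4 share 10 points from one half. The shift is therefore at most 0.10 × 30 + 0.10 × 20 = 5 points. With 5% and 15% in the HBOT arm it is 3 + 1 = 4 points.

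**5. Type I error.** Assume 45% at Stage 3 and 75% at Stage 4 in both arms (average 60% at a 50:50 mix). Exact Fisher enumeration over all allocations rejects in 2.4% of trials, the same as with no stage gap. Given a 12 v 8 split it rejects in 2.7%, and given 13 v 7 in 4.0%; both are below 5%.

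**6. Power.** Assume 45%/75% under usual care and 5%/15% under HBOT, which average to the planned 60% and 10%. Exact enumeration, two-sided 0.05:

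| Stage 4: HBOT v usual care | Pooled Fisher | Stage-stratified exact |
|---|---|---|
| 10 v 10 | 91.6% | 92.1% |
| 12 v 8 | 85.4% | 93.0% |
| 13 v 7 | 81.5% | 90.5% |

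If stage has no effect (60% v 10% in both stages), pooled Fisher has 90.8% and the stratified test 90.2% to 91.0% over the same splits.

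**The case against.** The strongest reply is that the driving input is missing. The 2- to 4-fold range, 30% to 60%, expresses uncertainty about one rate for the severe group as a whole. A reader might take 30% as the Stage 3 risk and 60% as the Stage 4 risk, but nothing in the protocol supports that split. It would also conflict with the planned 60% usual-care rate, since a 50:50 mix would give 45%. Nor does the protocol rank Stage 4 above Stage 3: its spectrum refers to involvement across all plaques, and the entry rule groups both stages as extensive. Requiring no improvement at a second bronchoscopy may narrow the prognostic spread further. All of this stands, so the size can only be given over a range of gaps.

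The consequence is also small. Six points is about half a standard error, or roughly one patient in 20. The protocol is silent on stratification, which is not the same as stating that a single envelope series is used. The planning rates concern stenosis, a secondary outcome; no stent rate is given, so the size for the primary airway outcome is unknown. These points stand too.

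Finally, stratified envelopes would by themselves largely prevent the imbalance, and with balanced stages the stratified test gains only half a point of power (92.1% v 91.6%). That is fair. The test still protects if some imbalance remains, and costs less than one point if stage proves irrelevant.

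**Conclusion.** The point holds as a minor, optional improvement. Entry pools two stages, stage is assessed before randomisation, and neither the described allocation nor the analysis uses it. A difference of 4 or more Stage 4 patients between arms is fairly likely (about 24% to 34%, given 20 per arm and 20% to 50% at Stage 4). What it does to the result depends on a stage gap that the documents do not give. With no HBOT effect, a difference of 4 shifts the risk difference by 6, 4 or 2 points at gaps of 30, 20 or 10; under the planned rates, a 12 v 8 split shifts it by at most about 5 points at the 30-point gap. Under the assumed 45%/75% v 5%/15% rates, power falls from 92% to 85% when a 12 v 8 split goes against HBOT.

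A reader might infer that the trial is biased, that its false-positive rate is inflated, or that a shift of 6 points or more is to be expected. The documents and the enumeration support none of these. Chance imbalance leaves the overall type I error at 2.4%. A 6-point shift needs, for example, a 30-point gap in both arms with a difference of 4 patients. What is lost is precision, and a prepared answer if the arms turn out unequal in stage.

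**What to change.** Prepare two envelope series, one for Stage 3 and one for Stage 4, each 1:1 in randomly varied blocks. Use the stage at the qualifying follow-up bronchoscopy, because a Stage 3 patient may have worsened to Stage 4 by then. With blocks no larger than 4 (an assumed size), Stage 4 counts differ by at most 2 between arms, for example 11 v 9, which limits the shift to 0.10 × 30 = 3 points at the 30-point gap.

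Add one line to the Data Analysis section: stent placement and stenosis are compared with a stage-stratified exact test, and the pooled Fisher table and stage by arm are reported alongside.

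The cost is slightly more envelope preparation and that line of text. No new procedure is needed, since entry already requires a grade and a judgement of improvement or worsening. The downside is that an incomplete last block in each series may leave the arms one or two patients off 20:20.

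### Allocation by selecting a prepared envelope, with no order, sealing, log or independent holder stated, does not secure concealment in a trial with no blinding described

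*Combined protocol and SAP*

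**What the plan says.** The whole allocation procedure stands under SUBJECT ENROLLMENT.

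- **First approach (Randomization).** Once patients are eligible, "they will be questioned as to their interest in participating in the study by the treating physician".
- **Consent (Randomization).** "Those interested will be approached by the study coordinator for informed consent".
- **Allocation (Randomization).** After consent, "subjects will be randomized to usual care or HBOT by selection of a pre-prepared envelope containing the randomization assignment".
- **Ratio and size (Randomization).** "We will target a total enrollment of 40 subjects with 1:1 enrollment to either HBOT or usual care".
- **Discretion before allocation (Exclusion Criteria).** Subjects deemed "too clinically unstable to be transported safely to the hyperbaric facility by their treating physicians will be excluded from enrollment".

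Two other places bear on the point. Airway Surveillance confirms that "the patients randomized to receive usual care will not undergo HBOT", and no sham session or blinding of clinicians, assessors or analysts is described anywhere. BACKGROUND records the team's impression of its own experience with HBOT: "We perceive that use of this technique has hastened resolution of the pseudomembranes, improved infectious complications and decreased the incidence of CAS".

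No other section adds to the allocation procedure.

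**The concern.** The only mechanism named is selection from a prepared set, and nothing ties a particular envelope to a particular patient. The text does not exclude choosing among envelopes, returning one, or keeping count of what remains. Concealment is therefore left to local habit.

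The setting makes this matter more. Because usual care involves no chamber sessions, staff at the one recruiting health system can see past assignments. They could anticipate later ones if the sequence is restricted. Enrolment also passes through two judgements by treating physicians before allocation. The first-named primary outcome, stent placement, is a clinical decision, and the primary investigators analyse the data, so no later blinded step offsets an imbalance made at entry. Intention-to-treat analysis keeps the groups as they were formed; it cannot restore comparability if they were formed by selection.

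**Working it through.** **1. The plan's own figure.** The documents give no figure for allocation. The sample size is the only related number. With 60% against 10%, two-sided 0.05 and 80% power, the pooled mean is 0.35 and

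n = [1.960 × √(2 × 0.35 × 0.65) + 0.842 × √(0.6 × 0.4 + 0.1 × 0.9)]² / 0.50² ≈ 13.04, rounded up to 14 per group.

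The stated 14 reproduces. Nothing in it depends on how patients are allocated, so the fix leaves it and the target of 40 unchanged.

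**2. How predictable the next arm is.** This depends on a scheme the plan does not state. Suppose an observer sees all past assignments and always guesses the arm with more envelopes left. If a envelopes of one arm and b of the other remain, the chance of a correct guess is max(a, b)/(a + b), averaged over all paths.

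| Scheme for 40 patients | Expected correct guesses |
|---|---|
| Simple randomization | 20 (50%) |
| One pool of 20 and 20 | 23.5 (58.7%) |
| Fixed blocks of 4 | 28.3 (70.8%) |

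For one block of 4: 1/2 + 2/3 + 2/3 + 1 = 2.83, times 10 blocks = 28.3. The fourth assignment is always known and the third is known one time in three, so 10 × (1 + 1/3) = 13.3 of 40 assignments are known in advance.

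**3. What steering could do.** Inputs: 20 per arm (40 at 1:1). The two risk levels come from DATA ANALYSIS AND STATISTICAL CONSIDERATIONS, where a 15% stenosis rate in all recipients is said to be 2 to 4 times higher in severe cases: 2 × 15% = 30% and 4 × 15% = 60%. Treating these as a lower-risk and a higher-risk half of the enrolled patients is an assumption made here, as is the absence of any treatment effect.

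Without steering, each arm has 10 patients of each kind. Exchange m lower-risk patients into HBOT for m higher-risk patients into usual care. The mean risks become

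- usual care: [(10 − m) × 0.3 + (10 + m) × 0.6] / 20
- HBOT: [(10 + m) × 0.3 + (10 − m) × 0.6] / 20

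The false difference is 2m × 0.3 / 20 = 0.03m. Each arm's event count is the sum of two independent binomials, one per risk level. Summing the joint probabilities of all tables with two-sided Fisher p ≤ 0.05 gives the rejection rate.

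| Exchanges m | Usual care | HBOT | False difference | Fisher rejects |
|---|---|---|---|---|
| 0 | 45% | 45% | 0 | 1.6% |
| 2 | 48% | 42% | 6 points | 2.4% |
| 4 | 51% | 39% | 12 points | 5.3% |
| 6 | 54% | 36% | 18 points | 11.3% |
| 10 (complete sorting) | 60% | 30% | 30 points | 34.7% |

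A simpler approximation, one binomial per arm at its mean risk, gives 2.2%, 3.1%, 6.2% and 12.1% for m = 0, 2, 4 and 6. The conclusion is the same.

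**The case against.** The strongest reply is that this is silence, not a defective method. An envelope prepared in advance with the assignment inside is compatible with sealed, opaque envelopes opened in order, and they may have been used that way. The coordinator obtains consent and an envelope is selected only afterwards; no text puts envelopes in a treating physician's hands. RISK/BENEFIT ASSESSMENT declares equipoise, and TREATMENT ARM CROSSOVER may make HBOT available to usual-care patients at 8 to 12 weeks if they meet its criteria, which weakens any motive to steer.

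Much of this stands, and it limits what can be said. It does not close the gap: whoever handles the envelopes is not bound to any order, and the consent step limits the physicians' influence without removing it.

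Three stronger readings are tempting and unsupported.

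- **That enrolment was steered, or that physicians choose the arm.** The documents show neither.
- **That a few steered patients suffice for a significant result.** Starting from an assumed 8/20 against 8/20, exchanging pairs gives 9/7, 10/6, 11/5 and 12/4, with two-sided Fisher p = 0.75, 0.33, 0.11 and 0.02. Four exchanges thus reach significance only if staff know at entry who will have the event within 12 months. They also mean 8 of 40 patients (20%) misplaced, all in the same direction. With knowledge of risk only, four exchanges give 5.3%.
- **That every outcome would be biased.** Steering on airway prognosis need not move biopsy-proven rejection, which is listed beside stent placement as primary.

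**Conclusion.** The point holds as a risk that is not ruled out. Selection of a prepared envelope, with no order, sealing, numbering, log or independent holder stated, does not secure concealed allocation. That the trial is unblinded is inferred from its design; open delivery does not itself break concealment, but it lets staff learn past arms.

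The size is moderate and conditional. Under the assumptions stated (no effect, 20 per arm, half at 30% and half at 60% risk), four to six exchanges produce a false difference of 12 to 18 points and a Fisher rejection rate of 5.3% to 11.3%, against 1.6% with none. The displaced estimate matters even where the test does not reject. The illustration uses stenosis risk, because the documents give no rate for stent placement. The change is a cheap improvement that is worth making.

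**What to change.** Replace the envelope-selection wording under Randomization with the following procedure.

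1. A computer-generated 1:1 sequence, either unblocked or with varied block sizes withheld from recruiting staff.
2. Assignments placed in sequentially numbered, opaque, sealed envelopes, prepared and held by existing staff who do not recruit.
3. After consent, the next number in order is used, with the subject ID and date written on the envelope before it is opened.
4. Every envelope is logged, including any unused or spoiled.

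The blocking rule is needed: a computer list in fixed blocks of 4 would be easier to foresee (70.8%) than one shuffled pool (58.7%). Simple randomization is the least predictable but can leave unequal arms; with 40 patients, a split of 14/26 or worse has probability 2 × P(X ≤ 14) = 8.1% for X binomial (40, 0.5).

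The cost is a few protocol sentences and minor one-time preparation. No visits or patients are added, and 14 per group with a target of 40 stays as it is.
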